11.0 CRITERIA FOR RESPONSE

Response will be assessed according to the 2008 IWCLL criteria.(7) Overall response is defined as a CR or PR. Patients with missing or no response assessment will be classified as non-responders. The full criteria are re-produced below. Please note that PET/CT or MRI can be performed for response assessment in lieu of CT scan, if these were performed for disease staging pre-treatment.

Criteria for Complete Remission (CR):

Requires all the following criteria to be met:

- Peripheral blood lymphocytes (evaluated by blood and differential count) below 4 x 10^9/L (4000/μL)
- Absence of significant lymphadenopathy (lymph nodes >1.5 cm in diameter) by CT (or PET) examination of neck, thorax, abdomen and pelvis
- No hepatomegaly or splenomegaly by physical examination (and CT/PET if assessment was abnormal before therapy or if physical exam is inconclusive)
- Absence of constitutional symptoms
- Blood counts above the following values:
 - Neutrophils more than 1.5 x 10^9/L (1500/μL) without need for exogenous growth factors
 - Platelets more than 100 x 10^9/L (100 000/ μ L) without need for exogenous growth factors

- Hemoglobin more than 110 g/L (11.0 g/dL) without red blood cell transfusion or need for exogenous erythropoietin
- Bone marrow aspirate and biopsy, demonstrating at least normocellular for age, with less than 30% of nucleated cells being lymphocytes. Lymphoid nodules should be absent. If the bone marrow is hypocellular, a repeat determination should be made in 4 weeks or when peripheral blood counts have recovered. Minimal residual disease will be assessed by 4 color flow cytometry from the bone marrow.

Patients who fulfill all the criteria for a CR, but who have a persistent anemia or thrombocytopenia or neutropenia apparently unrelated to CLL but related to drug toxicity are classified as complete remission with incomplete blood count recovery (CRi).

Criteria for Partial Remission (PR).

To meet criteria for PR the patient must have achieved at least one of criteria 1-3, below (if abnormal before therapy), as well as one or more of the features listed in section 4, below.

- 1. A decrease in the number of blood lymphocytes by 50% or more from the value before therapy.
- Reduction in lymphadenopathy as measured by PET/CT) as defined by the following:
 - A decrease in lymph node size by 50% or more either in the sum products of up to 6 lymph nodes, or in the largest diameter of the enlarged lymph node(s) detected prior to therapy.
 - No increase in any lymph node, and no new enlarged lymph node. In small lymph nodes (</=2 cm), an increase of less than 25% is not considered to be significant.
- 3. A reduction in the noted pretreatment enlargement of the spleen or liver by 50% or more, as detected by CT scan.
- 4. The blood count should show one or more of the following results:
 - Neutrophils more than 1, without need for exogenous growth factors.
 - Platelet counts greater than 100 x10⁹/L (100 000/μL) or 50% improvement over baseline without need for exogenous growth factors.
 - Hemoglobin greater than 110 g/L (11.0 g/dL) or 50% improvement over baseline without requiring red blood cell transfusions or exogenous erythropoietin.

Criteria for Stable Disease:

Stable disease is defined as not meeting criteria for complete remission, partial remission or progressive disease.

Criteria for Progressive Disease:

Progressive disease during or after therapy is characterized by at least one of the following:

- Lymphadenopathy. Appearance of any new lesion (>1.5cm) or increase by 50% or more in greatest determined diameter of any previous site.
- 2. An increase in the previously noted enlargement of the liver or spleen by 50% or more or the de novo appearance of hepatomegaly or splenomegaly.
- 3. An increase in the number of blood lymphocytes by 50% or more with at least 5000 B lymphocytes per microliter.
- 4. Occurrence of cytopenia (neutropenia, anemia, or thrombocytopenia) attributable to CLL.
- 5. After treatment, the progression of any cytopenia (unrelated to autoimmune cytopenia), as documented by a decrease of HGB levels by more than 20 g/L (2 g/dL) or to less than 100 g/L (10 g/dL), or by a decrease of platelet counts by more than 50% or to less than 100 x 10^9/L (100 000/μL), which occurs at least 3 months after treatment, defines disease progression, if the marrow biopsy demonstrates an infiltrate of clonal CLL cells.

Minimal residual disease (MRD) analysis.

MRD will be assessed in bone marrow after 6, 12, and 24 months, using a standardized 4-color flow cytometry assay, with a sensitivity of 0.01%.(28) Patients will be categorized as MRD-negative or MRD-positive.

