Diarrhea is the most frequently reported non-hematologic AE with ibrutinib monotherapy and combination therapy. Other frequently reported gastrointestinal events include nausea, vomiting, and constipation. These events are rarely severe and are generally managed with supportive therapies including antidiarrheals and antiemetics. Subjects should be monitored carefully for gastrointestinal AEs and cautioned to maintain fluid intake to avoid dehydration. Medical evaluation should be made to rule out other etiologies such as *Clostridium difficile* or other infectious agents. Should symptoms be severe or prolonged follow the protocol dose modification guidelines (see Section 7.1).

Rash

Rash has been commonly reported in subjects treated with either single agent ibrutinib or in combination with chemotherapy. Rash occurred at a higher rate in the ibrutinib arm than in the ofatumumab arm in study 1112. Most rashes were mild to moderate in severity. Isolated cases of severe cutaneous adverse reactions (SCARs), including Stevens-Johnson Syndrome (SJS) have been reported in subjects treated with ibrutinib. Subjects receiving ibrutinib should be observed closely for rashes and treated symptomatically, including interruption of the suspected agent as appropriate. In addition, hypersensitivity-related events erythema, urticarial and angioedema have been reported.

Lymphocytosis

Upon initiation of single agent treatment with ibrutinib, a reversible increase in lymphocyte counts (i.e., ≥50% increase from baseline and an absolute count >5000/µL), often associated with reduction of lymphadenopathy, has been observed in most subjects (66%) with CLL/ small lymphocytic lymphoma (SLL) treated with ibrutinib as single agent. This effect has also been observed in some subjects with MCL (35%) treated with ibrutinib. This observed lymphocytosis is a pharmacodynamic effect and should not be considered progressive disease in the absence of other clinical findings. In both disease types,

lymphocytosis typically occurs during the first month of ibrutinib therapy and typically resolves within a median of 8.0 weeks in subjects with MCL and 14 weeks in subjects with CLL/SLL (range 0.1-104 weeks).

When ibrutinib was administered in combination with BR or with obinutuzumab in subjects with CLL/SLL, lymphocytosis was infrequent (7% with ibrutinib + BR versus 6% with placebo + BR and 7% with ibrutinib + obinutuzumab versus 1% with chlorambucil + obinutuzumab)

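### Section 11 item 3 scores a lymphocyte rise alone as progression during therapy, while Section 6.7 calls nearly the same finding a drug effect; the two need reconciling before PFS is scored

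*Combined protocol and SAP*

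**What the plan says.** Section 11 adopts the 2008 IWCLL criteria and tells the reader that "The full criteria are re-produced below". Its progression list opens: "Progressive disease during or after therapy is characterized by at least one of the following". Item 3 of that list is "An increase in the number of blood lymphocytes by 50% or more with at least 5000 B lymphocytes per microliter". No reference value, confirmation rule, drug-effect exception or pointer to another section is attached.

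Section 6.7, under Lymphocytosis, describes a reversible rise of at least 50% from baseline with an absolute count above 5000/µL. It says this "has been observed in most subjects (66%) with CLL"/SLL on single-agent ibrutinib, is "often associated with reduction of lymphadenopathy", and that "lymphocytosis typically occurs during the first month of ibrutinib therapy", with median resolution at 14 weeks in CLL/SLL (range 0.1 to 104 weeks). It then states: "This observed lymphocytosis is a pharmacodynamic effect and should not be considered progressive disease in the absence of other clinical findings".

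Three other sections bear on this. Section 5.2 ends ibrutinib at disease progression. Section 12.1.6 says asymptomatic treatment-related lymphocytosis is not an adverse event and that these patients stay on treatment. Section 13 lists clinically significant progression as a reason for removal from the study.

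PFS at 2 years is a secondary endpoint (Section 1.2). Section 15.4 estimates it by Kaplan-Meier and compares each patient's observed PFS with an individual prediction. It does not define the PFS event.

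**The concern.** Section 11 is the only list of progression criteria in the protocol, and it presents itself as complete. Someone scoring PFS from it would date progression at the first qualifying lymphocyte count. Section 6.7 says that count usually reflects the drug working. The two sections thus give opposite answers for the same patient.

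The situation is foreseeable. The rise tends to begin in month 1, and Section 10 schedules blood counts at day 28 of cycles 1, 2 and 3. Events scored this way would fall early and would lower both the 2-year PFS estimate and the observed-versus-predicted comparison.

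There is also a clash within Section 11. One nodal route to partial remission is "A decrease in lymph node size by 50% or more either in the sum products of up to 6 lymph nodes". A patient whose nodes shrink that much, who meets the blood-count condition for PR and whose lymphocyte rise persists, can satisfy both PR and PD. Section 11 does not say which prevails, so the 6-month response rate could be affected as well.

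**Working it through.** **Do the passages describe the same finding?**

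| | Section 11 item 3 | Section 6.7 |
|---|---|---|
| Size of rise | 50% or more, reference value not stated | 50% or more from baseline |
| Count | at least 5000 B lymphocytes/µL | absolute count above 5000/µL |
| When | during or after therapy | typically from month 1; median resolution 14 weeks |
| Status | progression by itself | not progression without other clinical findings |

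The definitions are nearly, not exactly, the same: one counts B lymphocytes, the other uses an absolute lymphocyte count. A rise driven by CLL cells would normally meet both.

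**The plan's own figure.** The documents give no precision or power target for PFS. The one stated figure is 78% power for the primary test (Section 15.2: n = 50, 16% versus 30%, one-sided 0.05). The exact binomial rule is at least 13 of 50, with size 0.0475 and power 0.777, so that figure reproduces and is not in dispute.

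**Inputs for an illustration.**
- n = 50 (Section 15.1).
- 24-month PFS, S, of 89% or 96%, the two first-line figures cited in Section 3.5.
- Assumptions: Section 11 progression is the PFS event, there is no censoring, and being scored on item 3 is independent of true progression.

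**Effect per patient.** If k patients are scored as progressed on lymphocytes alone, PFS becomes S × (1 − k/n), a fall of S × k/n. For k = 1 the fall is 0.89/50 = 1.78 points or 0.96/50 = 1.92 points.

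**How many patients take PFS below its own lower 95% limit?** The bias is downward, so the lower arm of the interval (S minus the lower limit) is the relevant distance. The number needed is that arm divided by the fall per patient, rounded up.
- Wilson: lower limit = [S + z²/2n − z√(S(1−S)/n + z²/4n²)] / (1 + z²/n), with z = 1.96.
- Clopper-Pearson: the 2.5% quantile of Beta(nS, n − nS + 1). At 89%, nS = 44.5, used as it stands.
- Log-log: S^exp(z·se), with se = √((1−S)/(nS)) / |ln S|.

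| S | Method | Lower limit | Lower arm (points) | Arm ÷ fall per patient | Patients |
|---|---|---|---|---|---|
| 89% | Wilson | 77.4% | 11.6 | 6.5 | 7 |
| 89% | Clopper-Pearson | 76.9% | 12.1 | 6.8 | 7 |
| 89% | Log-log | 76.4% | 12.6 | 7.1 | 8 |
| 96% | Wilson | 86.5% | 9.5 | 4.9 | 5 |
| 96% | Clopper-Pearson | 86.3% | 9.7 | 5.1 | 6 |
| 96% | Log-log | 84.9% | 11.1 | 5.8 | 6 |

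**Range by proportion scored.** The proportion is not in the documents, so it is varied here:
- 20% scored: 0.89 × 0.80 = 71% and 0.96 × 0.80 = 77%.
- 50% scored: 0.89 × 0.50 = 45% and 0.96 × 0.50 = 48%.
- 66% scored (50 × 0.66 = 33 patients): 0.89 × 0.34 = 30% and 0.96 × 0.34 = 33%.

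The last line is the literal upper bound on the effect if the Section 6.7 frequency carried over to this population and every such patient were scored on item 3.

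**The case against.** The protocol is not silent. Section 6.7 speaks in endpoint terms and is specific to this drug, whereas item 3 is a general CLL criterion. Section 12.1.6 points the same way: Section 5.2 ends treatment at progression, so keeping these patients on treatment makes sense only if the rise is not progression. An assessor who knows Section 6.7 will score PFS correctly. PFS is also secondary, with no hypothesis test attached.

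Most of this stands, and it limits the point to a conditional bias in secondary endpoints. It does not remove the conflict. Sections 12.1.6 and 13 govern treatment and study participation, not scoring, and a reported endpoint should not depend on whether the assessor imports a sentence from a drug-safety section into a list described as complete.

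Three stronger readings are tempting and are not supported:
- A reader might infer that PFS will collapse to about 30%. That needs every affected patient to be scored against Section 6.7. The 66% also comes from a general CLL/SLL summary, not from this early-stage population.
- A reader might take the symmetric normal half-width and conclude that 3 to 5 patients suffice. The half-widths are 8.7 points at 89% and 5.4 at 96%, against 5 × 1.78 = 8.9 and 3 × 1.92 = 5.8. At 96% that interval reaches 101.4%, so it understates the distance on the lower side.
- A reader might infer that the primary endpoint loses power because patients scored as progressed stop treatment. The CR/CRi criteria do not use item 3, and Section 12.1.6 keeps these patients on treatment.

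The effect on the 6-month response rate is doubly conditional: the rise must outlast its 14-week median, and PD must be taken to override PR.

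**Conclusion.** The contradiction is real and should be fixed. Applied as written, item 3 can turn a documented drug effect into a PFS event, and nothing in Section 11 or 15.4 prevents it.

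The number of patients who would be scored this way cannot be obtained from the documents. Under the stated assumptions, each one costs 1.8 to 1.9 points of 24-month PFS. It takes 5 to 6 patients (at 96%) or 7 to 8 (at 89%) to move the estimate beyond its lower 95% limit. That yardstick is a choice made here; the plan sets no precision target for PFS. The 30% to 33% figure is a bound and not a forecast.

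The bias reaches 2-year PFS, the observed-versus-predicted comparison and, conditionally, early response rates. It disappears if assessors apply Section 6.7.

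**What to change.** In Section 11 item 3, carry over or cross-refer to the existing Section 6.7 statement. Treatment-related lymphocytosis as described there, without other clinical findings, would then not by itself be scored as a PFS event and would not by itself override a response.

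An exception confined to endpoint scoring would leave two meanings of progression in the protocol. Sections 5.2, 6.7, 11, 12.1.6 and 13 therefore need to be reconciled so that the term has one meaning throughout. No clinical rule is proposed here.

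The cost is one sentence in Section 11 plus the reconciliation, with no new visit, sample or change in sample size. There is a small downside: some true progression that shows only as a lymphocyte rise may be dated later.

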12.0 ADVERSE EVENT REPORTING

Toxicities will be graded according to the NCI Expanded Common Toxicity Criteria (v4.03 or higher).(31)

12.1 Leukemia-specific Adverse Event Recording and Reporting Guidelines

These guidelines serve to bring the Department of Leukemia in compliance with the institutional policy on Reporting of Serious Adverse Events.

An adverse event is any untoward medical occurrence that may present during treatment with a pharmaceutical product but which does not necessarily have a causal relationship with this treatment. An adverse drug reaction is a response to a drug which is noxious and unintended, and which occurs at doses normally used in man for prophylaxis, diagnosis, or therapy of disease or for the modification of physiologic function.

Assessing causal connections between agents and disease is fundamental to the understanding of adverse drug reactions. In general, a drug may be considered a contributory cause of an adverse event if, had the drug not been administered, 1) the event would not have happened at all, 2) the event would have occurred later than it actually did, or 3) the event would have been less severe.

The Investigator or physician designee is responsible for verifying and providing source documentation for all adverse events and assigning the attribution for each event for all patients enrolled on the trial.

12.1.1 Adverse events will be documented in the medical record and entered into PDMS/Core.

12.1.2 These guidelines will be followed for the recording and reporting of adverse and serious adverse events.

- Baseline events will be recorded in the medical history section of the case report form and will include the terminology event name, grade, and start date of the event.
 - Baseline events are any medical condition, symptom, or clinically significant lab abnormality present before the informed consent is signed
 - Hematologic laboratory abnormalities will not be recorded as baseline events for patients with acute leukemia, myelodysplastic syndrome, chronic lymphocytic leukemia, or chronic myeloid leukemia in blast phase.
- If exact start date is unknown, month and year or year may be used as the start date of the baseline event. The maximum grade of the adverse event will be captured per course or protocol defined visit date.
- These adverse events will be recorded:

- Any grade adverse event that is possibly, probably, or definitely related to the study drug(s).
- All serious adverse events regardless of attribution to the study drug(s).
- Any grade adverse event regardless of attribution to the study drug(s) that results in any dose modification.
- Serious adverse events will be reported according to institutional policy.
- Protocol specific language regarding the recording and reporting of adverse and serious adverse events will be followed in the event of discordance between the protocol and Leukemia-specific adverse event recording and reporting guidelines.
- **12.1.3** For abnormal hematologic and chemical values, the apogee or nadir (whichever is appropriate) will be reported per course on the case report form. Please note that hematologic AEs will be graded according to NCI-WG/IWCLL criteria, which take into account the potential for abnormal pre-treatment values (Appendix N).
- **12.1.4** All adverse events will be collected for the purpose of grading, and determining attribution to study drugs by the PI using the following scale:
 - Unrelated: The AE is clearly NOT related to the intervention.
 - Unlikely: The AE is doubtfully related to the intervention.
 - Possible: The AE may be related to the intervention.
 - Probable: The AE is likely related to the intervention.
 - Definite: The AE is clearly related to the intervention.
- **12.1.5** All grade 3 and greater non-hematological events that are felt to be related to protocol treatment drugs will be documented on the toxicity log. The toxicity log data must reflect the relationship to the drug the event is felt to be related to.
- **12.1.6** The following are NOT considered AEs:
 - Pre-existing condition: A pre-existing condition (documented on the medical history CRF) is not considered an AE unless the severity, frequency, or character of the event worsens during the study period.
 - Pre-planned or elective hospitalization: A hospitalization planned before signing the ICF is not considered an SAE, but rather a therapeutic intervention. However, if

during the pre-planned hospitalization an event occurs, which prolongs the hospitalization or meets any other SAE criteria, the event will be considered an SAE. Surgeries or interventions that were under consideration, but not performed before enrollment in the study, will not be considered serious if they are performed after enrollment in the study for a condition that has not changed from its baseline level. Elective hospitalizations for social reasons, solely for the administration of chemotherapy, or due to long travel distances are also not SAEs.

- Diagnostic Testing and Procedures: Testing and procedures should not to be reported as AEs or SAEs, but rather the cause for the test or procedure should be reported.
- Asymptomatic Treatment Related Lymphocytosis: This event should also not be considered an AE. Subjects with treatment-related lymphocytosis should remain on study treatment and continue with all study-related procedures

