- (4) Medical history. Medical and surgical history and demographic information will be recorded. Medical and surgical history includes diagnoses, therapies, and medical and surgical treatments. A complete medical history will be obtained at screening/baseline, prior to first administration of study drug and at the end-of-treatment visit. At all other visits, the medical history taking can be focused to the needs of the patient but should pay particular attention to adverse events that are potentially related to ibrutinib, infections, and disease-related symptoms. During the CoVID19 epidemic, medical history may be obtained by the patient's M.D. Anderson Physician in a telephone or videoconference interview and documented in the chart.
- (5) Physical examination, including vital signs. Vital signs are temperature, pulse, respiratory rate, and blood pressure (when the patient is seated). A complete physical examination, including measurement of weight, must be performed at screening/baseline, prior to the first administration of study drug, and at the end-of-treatment Visit. Height need only be recorded at the initial visit. Following the screening/baseline physical examination, with the exception of the end-of-treatment Visit, all subsequent physical examinations can be focused to the individual needs of the individual patient. Given that, during the CoVID19 epidemic, many patients will not be able to come to M.D. Anderson, some assessments may be conducted remotely. Wherever possible, patients should have a physical exam at least every 6 months and, if unable to come to M.D. Anderson, this should be done by a local physician and the records obtained. If even this is not possible, the reasons for this should be documented in the patient's chart.
- (6) Concomitant medications. These will be recorded in the electronic medical record.
- (7) Complete blood count with differential. CBC with differential is defined as peripheral blood total white blood cell (WBC) count, hemoglobin, hematocrit, platelet count, absolute neutrophil count (ANC), and WBC differential, reported individually for each cell type. Hematologic assessments must be obtained at screening and at every subsequent assessment, as specified in the Schedule of Events, or more frequently as clinically indicated (e.g. to confirm loss of hematologic response as defined in section 9.1).

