12.1.9 Serious Adverse Event Reporting (SAE)

12.1.9.1 Definition of an SAE:

An adverse event or suspected adverse reaction is considered "serious" if, in the view of either the investigator, it results in any of the following outcomes:

- Death
- A life-threatening adverse drug experience; this is defined as any adverse
 experience that places the patient, in view of the initial reporter, at immediate risk of
 death from the adverse experience, as it occurred. It does not include an adverse
 experience that, had it occurred in a more severe form, might have caused death.
- Inpatient hospitalization or prolongation of existing hospitalization.
- A persistent or significant incapacity or substantial disruption of the ability to conduct normal life functions.
- A congenital anomaly/birth defect.

12.1.9.2 Important medical events:

Important medical events that may not result in death, be life-threatening, or require hospitalization may be considered a serious adverse drug experience when, based upon appropriate medical judgment, they may jeopardize the patient or subject and may require medical or surgical intervention to prevent one of the outcomes listed in this definition. Examples of such medical events include allergic bronchospasm requiring intensive treatment in an emergency room or at home, blood dyscrasias or convulsions that do not result in inpatient hospitalization, or the development of drug dependency or drug abuse (21)

CFR 312.32). Pregnancy, drug overdose, and secondary malignancy will be handled as SAE. Important medical events as defined above, may also be considered serious adverse events. Any important medical event can and should be reported as an SAE if deemed appropriate by the Principal Investigator

12.1.9.3 SAE reporting:

- All SAEs should be reported to the study nurse or the Principal Investigator [[name]., Ph.D, [contact] or [contact]] within 24 hours of observing or learning of the event.
- All AEs should be reported to the study nurse.
- Expected therapy-related events include those known toxicities or side effects of ibrutinib. These grade 4 or less events, including, but not limited to diarrhea, atrial fibrillation, infection, hemorrhage, hypertension and joint pain/arthralgia will not be reported as individual SAEs, but will be summarized in the annual report to the IRB. However, these will be reported to Pharmacyclics within 24 hours of knowledge of the event.

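### Section 12.1 does not settle whether non-serious adverse events judged unrelated or unlikely, without a dose change, enter the database; if they do not, any-grade infection, minor bleeding and cardiac rates are recorded too low

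*Combined protocol and SAP*

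**What the plan says.** Section 12.1.2 names three kinds of event to be recorded. One is defined by causality: "Any grade adverse event that is possibly, probably, or definitely related to the study drug(s". The other two apply whatever the cause is judged to be: events that are serious, and events of any severity that led to a change of dose.

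A non-serious event rated Unrelated or Unlikely that leads to no dose change is in none of the three.

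Three neighbouring provisions carry no such limit. Section 12.1.1 says: "Adverse events will be documented in the medical record and entered into PDMS/Core". Section 12.1.4 says: "All adverse events will be collected for the purpose of grading, and determining attribution to study drugs by the PI using the following scale", and the five-level scale that follows begins with Unrelated and Unlikely. Section 12.1.9.3 says: "All AEs should be reported to the study nurse".

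Note 4 to the schedule in Section 10.0 adds that history-taking at interim visits "should pay particular attention to adverse events that are potentially related to ibrutinib, infections, and disease-related symptoms". It names infections separately from events thought to be due to ibrutinib.

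**The concern.** Section 12.1 gives two answers to a plain data-management question, and staff could reasonably follow either. Under the narrower answer, whether a non-serious event is counted depends on the PI's causality judgement.

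That matters more here than in most trials, for three reasons.

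- There is no control arm (Section 15.1), so nothing inside the trial would show the effect of the filter.
- Section 3.3 says that early-stage CLL itself carries infection risk and suggests that a non-immunosuppressive agent might lower it. The cause of any single infection is therefore uncertain, and leaving out the doubtful ones moves the rate in the direction that favours the rationale.
- The patients have no indication for treatment (Section 4.1), so low-grade tolerability bears on whether early treatment is worthwhile. Hypothesis 3 itself expects less tolerance of troublesome side effects in this group.

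**Working it through.** **Figures in the plan.** The plan states no figure on this point. The one computed design figure, 78% power in Section 15.2, reproduces. With 50 patients, rates of 16% and 30%, and a one-sided exact binomial test, the smallest rejection count is 13, with type I error 0.0475 and power 77.7%. It does not depend on adverse event recording.

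**Which events are captured whatever their attribution.**

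1. Serious events and events causing a dose modification: 12.1.2.
2. Major hemorrhage, meaning grade 3 or higher, any serious bleed, or any central nervous system bleed: 12.1.10, regardless of seriousness and with no attribution condition.
3. New malignancies: 12.1.8.
4. Per-course extremes of hematologic and chemistry values: 12.1.3.

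What remains exposed is non-serious infection, minor bleeding, cardiac events and hypertension, when rated Unrelated or Unlikely and followed by no dose change.

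**Is grade 3 covered through the dose-modification route?** Section 7.3 calls for interruption at grade 3 or higher non-hematological toxicity, which would bring such events in if an interruption counts as a dose modification. This is not assured. Section 7.0 presents 7.1-7.3 as recommendations for toxicity associated with ibrutinib and lets the investigator depart from them. A grade 3 event judged unrelated may therefore lead to no dose change. The toxicity log in 12.1.5 does not close the gap, because it too is limited to events felt to be related.

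**Does the precedence clause decide?** Section 12.1.2 lets protocol-specific wording prevail over the departmental guidelines. All the conflicting provisions sit under those same guidelines in 12.1, so the clause does not choose between them.

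**Direction and size.** Let *u* be the share of non-serious, non-dose-modifying infections rated Unrelated or Unlikely, and *s* the share of all infections that are serious or dose-modifying. The shortfall in the infection count is *u*(1 − *s*). It is never negative, so the filter can only lower the count. The documents give neither *u* nor *s*. On assumed values:

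| *s* | *u* = 20% | *u* = 60% |
|---|---|---|
| 0% | 20% | 60% |
| 30% | 0.20 × 0.70 = 14% | 0.60 × 0.70 = 42% |
| 50% | 0.20 × 0.50 = 10% | 0.60 × 0.50 = 30% |

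A patient-level illustration, also on assumptions: suppose 20 of 50 patients (40%, exact 95% CI 26-55%) each have one non-serious infection without a dose change.

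| Judged at least possibly related | Recorded | Rate (exact 95% CI) |
|---|---|---|
| 25% | 5/50 | 10% (3-22%) |
| 50% | 10/50 | 20% (10-34%) |
| 75% | 15/50 | 30% (18-45%) |

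Patients with several infections would be missed less often than this.

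**The case against.** The strongest reply is that the sections can be read in sequence: 12.1.4 collects every event so that it can be graded and attributed, and 12.1.2 then says which are recorded. On that reading there is a defined departmental rule and no contradiction. The reading is possible, but 12.1.1 sends adverse events to the database without restriction, so it is not the only one.

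A second reply is that few events would be lost. Section 12.1.9.3 names infection, atrial fibrillation, hemorrhage and hypertension among the expected effects of ibrutinib, and the Possible category requires only that the drug may be involved. This stands as a reason to think the loss could be small. It does not show that it is.

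Third, no planned analysis is harmed. Infection, bleeding and cardiac rates are not endpoints, and Section 15 contains no safety analysis. That stands.

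Some stronger readings are tempting but not supported:

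- *All bleeding rates are filtered, so comparison with the cited 2.5% grade 3-4 hemorrhage fails.* Section 12.1.10 captures those events without regard to attribution.
- *Comparison with the cited 6% atrial fibrillation is shown to be invalid.* The documents do not say whether that figure is all-cause.
- *The total infection count is short by the full share judged unrelated.* Serious and dose-modifying infections are recorded anyway, so the shortfall is smaller, as the factor (1 − *s*) shows.
- *The lost events cannot be recovered.* Section 12.1 requires source documentation and attribution for all adverse events, so re-abstraction from charts is possible, though laborious.

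**Conclusion.** The inconsistency is real but limited in reach. If 12.1.2 governs, some non-serious infections, minor bleeds, cardiac events and hypertension may be missing from the database. These would be mainly grade 1-2, with grade 3 not excluded. Any-grade rates of these events would then be lower than the all-cause rates. The direction is certain because the filter only removes events. The size cannot be estimated from the documents, and the percentages above are illustrations.

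The harm would fall on later safety reporting. It would not touch the primary CR/CRi test, the power or any analysis in Section 15. The change is still worth making because it is cheap: 12.1.4 already has every event collected, graded and attributed.

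**What to change.** Reconcile 12.1.1, 12.1.2 and 12.1.4 so that they state one rule for database entry. Preferably, enter events regardless of attribution and hold attribution as a data field. At a minimum, do so for all infections, bleeding, cardiac events and hypertension of any grade, and for every event of grade 3 or higher. Report all-cause rates first and treatment-related rates second.

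If the filter is kept on purpose, say so in 12.1.2, label the any-grade rates as treatment-related, and do not set them against all-cause rates from other studies.

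The cost is an amendment to the recording list in 12.1.2, matching wording in the two neighbouring sections, and some added data entry. No new visits or tests are needed. Reported toxicity rates will be somewhat higher than under the filter.
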